5.4.4.1. Prohibited Concomitant Therapy for Pembrolizumab (Part C)

Systemic glucocorticoids are prohibited for any purpose other than the following:

- To modulate symptoms from an event of clinical interest of suspected immunologic etiology
- As supportive care during transfusion or administration of G-CSF (Section 5.4.2.2).
- For the prevention of emesis
- To premedicate for IV contrast allergies
- To treat chronic obstructive pulmonary disease (COPD) exacerbations (only short-term oral or IV use in doses >10 mg/day prednisone or equivalent)
- For chronic systemic replacement not to exceed 10 mg/day prednisone equivalent
- Other glucocorticoid use except when used for the following purposes:
 - For topical use or ocular use
 - Intraarticular joint use
 - For inhalation in the management of asthma or COPD

The use of physiologic doses of corticosteroids may be approved after consultation with the sponsor.

5.5. Management of Adverse Reactions

5.5.1. Management of Infusion Reactions

5.5.1.1. LV

IRRs may occur during the infusion of study treatment. The infusion should be administered at a site properly equipped and staffed to manage anaphylaxis should it occur. Routine premedication should not be administered for the prevention of IRRs prior to the first dose of LV.

All supportive measures consistent with optimal subject care should be given throughout the study according to institutional standards. Supportive measures may include extending the infusion time and/or administering medications for IRRs.

Subjects who have experienced a Grade 1 or Grade 2 IRR with LV should be premedicated for subsequent infusions.

Subjects who experience a Grade 3 IRR may potentially receive additional treatment with LV at the discretion of the investigator after discussion with the medical monitor.

Premedication for LV may include acetaminophen (or equivalent, eg, paracetamol), an antihistamine, and a corticosteroid administered 30–60 minutes prior to each infusion, or according to institutional standards.

If anaphylaxis or a Grade 4 IRR occurs, LV should be immediately and permanently discontinued.

See Section 7.6.1.2 for details regarding recording AEs of infusion reactions.

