5.2.4. Dose Modifications

5.2.4.1. Part A (q3wk dosing)

Dose modification guidelines for LV q3wk treatment-associated toxicity are described in [Table 9](#). The maximum doses after modifications are:

- 200 mg for subjects reduced to 2.0 mg/kg
- 150 mg for subjects reduced to 1.5 mg/kg

Table 9: Q3wk LV dose levels

Dose Level	Dose	Maximum Dose
Starting dose	2.5 mg/kg	250 mg
-1	2.0 mg/kg	200 mg
-2	1.5 mg/kg	150 mg

[Table 10](#) describes dose modifications for LV treatment-associated toxicity.

Doses reduced for LV-related toxicity should not be re-escalated.

If a subject has a clinically significant, unresolved AE on Day 1 of C2 or beyond, the start of the cycle may be delayed for up to 14 days. Delays of >14 days must be approved by the medical monitor.

In the event a subject is unable to tolerate their dose level, additional treatment cycles (C2 or later) may be administered at a lower dose level upon approval by the medical monitor.

Table 10: Dose modifications for LV-associated toxicity (Part A; q3wk dosing)

Toxicity	Grade 1	Grade 2	Grade 3	Grade 4
Peripheral neuropathy ^a	Continue at same dose level	Withhold until toxicity resolves to \leq Grade 1; then resume treatment at the next lower dose level	Withhold until toxicity resolves to \leq Grade 1, then resume treatment at the next lower dose level	Discontinue treatment
Non-hematologic ^a (except peripheral neuropathy and hyperglycemia)	Continue at same dose level	Continue at same dose level	Withhold dose until toxicity is \leq Grade 2 or has returned to baseline, then resume treatment at same dose level ^b	Withhold dose until toxicity is \leq Grade 2 or has returned to baseline, then reduce dose to the next lower dose level and resume treatment, or discontinue at the discretion of the investigator ^{b,c}
Hematologic ^a	Continue at same dose level	Continue at same dose level	Withhold until toxicity resolves to \leq Grade 2 or baseline ^{d,e} . For neutropenia, strongly consider G-CSF support , then resume treatment at the same dose level. Prophylactic G-CSF support should be strongly considered for subsequent cycles. (See Appendix G)	Withhold until toxicity resolves to \leq Grade 2 or baseline ^{d,e} . For neutropenia, strongly consider G-CSF support , then resume treatment at the same dose level. Prophylactic G-CSF support is required for all subsequent cycles. If Grade 4 neutropenia recurs despite G-CSF support, consider dose reduction to dose level -1 or discontinuation. (Appendix G)

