Non-hematologic ^a (except peripheral neuropathy and hyperglycemia)	Continue at same dose level	Continue at same dose level	Withhold dose until toxicity is \leq Grade 2 or has returned to baseline, then resume treatment at same dose level ^b	Withhold dose until toxicity is \leq Grade 2 or has returned to baseline, then reduce dose to the next lower dose level (see Table 11) and resume treatment, or discontinue at the discretion of the investigator ^{b,c}
Hematologic ^a	Continue at same dose level	Continue at same dose level	Withhold until toxicity resolves to \leq Grade 2 or baseline ^{d,e} , then resume treatment at the same dose level. If the dose is held >48 hours, the dose may be omitted and dosing may resume on the next scheduled dosing day. See Sections 5.4.2 and 5.4.3 on allowed concomitant therapy and myeloid growth factors.	Withhold until toxicity resolves to \leq Grade 2 or baseline ^{d,e} , then reduce dose to the next lower dose level (see Table 11) if treatment is resumed ^{b,c} . If the dose is held >48 hours, the dose may be omitted and dosing may resume on the next scheduled dosing day. If Grade 4 neutropenia recurs, reduce dose to the next lower dose level (see Table 11) if treatment is resumed, or discontinue at the discretion of the investigator. See Sections 5.4.2 and 5.4.3 on allowed concomitant therapy and myeloid growth factors.
Febrile neutropenia ^a	Not applicable	Not applicable	Withhold until febrile neutropenia resolves and neutrophil count returns to \leq Grade 2 or baseline and then resume treatment at the next lower dose level (see Table 11). If the dose is held >48 hours, the dose may be omitted and dosing may resume on the next scheduled dosing day. If febrile neutropenia recurs, reduce dose to the next lower dose level (see Table 11) if treatment is resumed, or discontinue at the discretion of the investigator. See Sections 5.4.2 and 5.4.3 on allowed concomitant therapy and myeloid growth factors.	

The maximum dose will be 200 mg per infusion for subjects enrolled in Part B and Part C (Arm 3).

- a Only 2 dose reductions are allowed without prior medical monitor approval. Additional toxicities should be managed with dose delays. Medical monitor approval is needed for further dose reduction.
- b Subjects who develop Grade 3 or 4 electrolyte laboratory abnormalities may continue study treatment without interruption if a management plan consistent with institutional practice and regular monitoring are put in place.

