- c Treatment should be discontinued for subjects who experience Grade 4 infusion-related reactions.
- d Support with blood product transfusions allowed per institutional standard of care.
- e Subjects who develop Grade 3 or 4 lymphopenia may continue study treatment without interruption.

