7.6.1.2. Procedures for Eliciting and Recording Adverse Events

Investigator and study personnel will report all AEs and SAEs whether elicited during subject questioning, discovered during physical examination, laboratory testing and/or other means by recording them on the CRF and/or SAE form, as appropriate.

Eliciting Adverse Events

An open-ended or non-directed method of questioning should be used at each study visit to elicit the reporting of AEs.

Recording Adverse Events

The following information should be recorded on the Adverse Events and Pre-existing Conditions CRF:

- Description including onset and resolution dates
- Whether it met SAE criteria
- Severity
- Relationship to study treatment or other causality
- Outcome

Diagnosis vs. Signs or Symptoms

In general, the use of a unifying diagnosis is preferred to the listing out of individual symptoms. Grouping of symptoms into a diagnosis should only be done if each component sign and/or symptom is a medically confirmed component of a diagnosis as evidenced by standard medical textbooks. If any aspect of a sign or symptom does not fit into a classic pattern of the diagnosis, report the individual symptom as a separate AE.

Important exceptions for this study are adverse reactions associated with the infusion of LV. For IRRs, do not use the NCI CTCAE terms of “cytokine release syndrome,” “acute infusion reaction,” or “allergic or hypersensitivity reaction.” Instead, record each sign or symptom as an individual AE. If multiple signs or symptoms occur with a given infusion-related event, each sign or symptom should be recorded separately with its level of severity.

Recording Serious Adverse Events

For SAEs, record the event(s) on both the CRF and an SAE form.

The following should be considered when recording SAEs:

- Death is an outcome of an event. The event that resulted in the death should be recorded and reported on both an SAE form and CRF.
- For hospitalizations, surgical, or diagnostic procedures, the illness leading to the surgical or diagnostic procedure should be recorded as the SAE, not the procedure itself. The procedure should be captured in the narrative as part of the action taken in response to the illness.

Progression of the Underlying Malignancy

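### Section 5.5.1.1 and the LV dose-modification tables (10, 12 and 14) do not match on anaphylaxis and Grade 3 infusion reactions, and nothing says which governs

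*Protocol*

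**What the plan says.** Protocol Section 5.5.1.1 deals specifically with infusion reactions to LV. Its stopping rule has two triggers: "If anaphylaxis or a Grade 4 IRR occurs, LV should be immediately and permanently discontinued". No grade is attached to anaphylaxis. For a Grade 3 IRR, the subject "may potentially receive additional treatment with LV at the discretion of the investigator after discussion with the medical monitor". For Grade 1 or 2 it asks for premedication at later infusions.

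The LV dose-modification guidance is in Section 5.2.4: Table 10 for Part A, Table 12 for Part B and Part C Arm 3, and Table 14 for Part C Arms 1 and 2. Each table has one general row for non-hematologic toxicity, with two exceptions: "except peripheral neuropathy and hyperglycemia". In all three, the Grade 3 cell of that row withholds LV until the event is Grade 2 or lower "or has returned to baseline, then resume treatment at same dose level". Footnote c, attached to the Grade 4 cell of the row, is the only statement about infusion reactions in the tables: "Treatment should be discontinued for subjects who experience Grade 4 infusion-related reactions".

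**The concern.** IRRs are not among the row's exceptions, and footnote c shows that the authors placed them in that row. A site that looks up a Grade 3 IRR in its table therefore finds an instruction to withhold and resume, and an IRR stopping rule that begins at Grade 4. Section 5.5.1.1 makes the same resumption depend on a decision taken after a discussion, and adds anaphylaxis as a separate reason to stop for good. At stake is whether a subject is re-exposed to LV after a serious infusion reaction, and whether that decision is reviewed first. No endpoint, sample size or analysis depends on it.

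**Working it through.** There is no figure to reproduce, so the check sets the texts side by side.

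| Event | Section 5.5.1.1 | Tables 10, 12 and 14 | Match? |
|---|---|---|---|
| Grade 1 or 2 IRR | Premedicate later infusions | Continue, same dose level | Compatible; 5.5.1.1 adds a step |
| Grade 3 IRR | Further LV possible, by investigator decision after medical monitor discussion | Withhold, then resume on recovery; no discussion step | No |
| Grade 4 IRR | Permanent stop | Stop (footnote c) | Yes |
| Anaphylaxis | Permanent stop, no grade given | Not mentioned | No |

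1. **Do IRRs belong in the general row?** Yes. Only neuropathy and hyperglycemia are excepted, and footnote c hangs on this row's Grade 4 cell.

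2. **What exactly differs at Grade 3?** It is not the dose. Section 5.5.1.1 names no dose level after a Grade 3 IRR, so the tables' same-dose wording contradicts nothing there. The difference is resumption on recovery alone against resumption only after a discretionary decision and a discussion.

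3. **Is anaphylaxis just another name for a Grade 4 IRR?** Section 5.5.1.1 lists the two as alternatives, so its text treats anaphylaxis as a separate trigger. Footnote c carries over only the Grade 4 trigger.

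4. **Do the tables send the reader to Section 5.5.1?** No, although they cross-refer where other sections govern. Hyperglycemia is sent to Section 5.6. Hematologic toxicity is sent to Sections 5.4.2 and 5.4.3 (Table 12) or Appendix G (Tables 10 and 14). The text around Tables 12 and 14 cites Section 5.5.3 on overlapping toxicities, but not 5.5.1. Section 5.5.1.1 does not point back to the tables either.

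5. **Does recording help or hinder?** Section 7.6.1.2 bars the collective terms for infusion reactions: "Instead, record each sign or symptom as an individual AE". A reaction held as several symptoms, each with its own grade, is easier to read through the general row symptom by symptom.

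6. **Which regimens are covered?** All of them. Planned enrolment by table (Section 9.1) is 72 for Table 10, 252 + 30 = 282 for Table 12 and 30 + 30 = 60 for Table 14, and 72 + 282 + 60 = 414. This is the planned maximum treated under the tables, not a count of subjects who would meet the mismatch.

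**The case against.** The strongest reply is that the protocol has a dedicated IRR rule and signposts it. Section 5.4.2.2 sends readers to Section 5.5.1 for managing infusion reactions. Section 5.5.1.3 speaks of two sets of IRR guidelines, one per drug, which suggests that 5.5.1.1 is the LV set. A specific rule would normally override a general table. For Grade 3 a site can also satisfy both texts: withhold, discuss and, if re-treatment is agreed, resume at the level the table gives. Footnote c can be read as removing the investigator's discretion at Grade 4, not as a complete list of IRR stopping rules.

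Much of this stands, and it limits the point. A reader might infer that the tables direct full-dose re-challenge after anaphylaxis, a direct contradiction touching all 414 subjects. The documents do not support that:

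- The tables are silent on anaphylaxis; they do not permit re-challenge.
- How anaphylaxis would be graded is not stated. Section 7.6.1.1 leaves the grading criteria to the study manual.
- The same-dose wording is not in conflict.
- Section 4.4.1 always allows treatment to be stopped for an adverse event or by investigator decision.
- 414 is planned enrolment.

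What the reply does not remove is that no order of precedence is written down, and that the signposts lie outside the tables a site uses for dosing. Being able to comply with both texts at Grade 3 also helps only a site that has read both.

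**Conclusion.** The inconsistency is real and present in all three tables. It has two parts: a Grade 3 IRR can be followed by LV on recovery alone under the tables but only after medical monitor discussion under Section 5.5.1.1, and the anaphylaxis trigger is missing from the tables. Grade 4 IRRs are handled consistently.

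Its size cannot be stated as a number of subjects, because the documents give no frequency of IRRs or anaphylaxis with LV. Per event, the difference is resuming LV against stopping it (anaphylaxis), or resuming without against with a prior discussion (Grade 3 IRR). The conclusion assumes that some sites would apply a table without also consulting Section 5.5.1.1; a site that treats 5.5.1.1 as the governing rule would not be misled. This is a mismatch between sections on clinical management, worth correcting because it bears on safety and the correction is small. It is not a statistical error, and no view is taken on which rule is right.

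**What to change.** The sponsor should reconcile footnote c and the Grade 3 non-hematologic cell of Tables 10, 12 and 14 with Section 5.5.1.1, and add a cross-reference to Section 5.5.1 in each table, as is already done for hyperglycemia, so that one rule governs IRRs and anaphylaxis under every LV regimen. The content of that rule is the sponsor's clinical decision.

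The cost is one footnote, one cell and one pointer in each of three tables. No endpoint, sample size or SAP analysis changes.

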5.5.1.2. Pembrolizumab

Details on IRRs for pembrolizumab are detailed in Section 5.3.4.2 and Table 16.

See Section 7.6.1.2 for details regarding recording AEs of infusion reactions.

5.5.1.3. Infusion-Related Reaction of Uncertain Cause

If a patient experiences an IRR after receiving both study treatments and a single cause of the IRR cannot be determined, both sets of guidelines for IRRs must be followed.

5.5.2. Management of Overdose

5.5.2.1. LV Overdose

In the event of an overdose of LV >10%, study personnel should:

- Care for and medically stabilize the subject until there is no immediate risk of complications or death, if applicable. The subject should be closely monitored for adverse reactions, particularly neutropenia. Supportive care per institutional standards should be administered. Adherence to current clinical practice guidelines for the use of G-CSF is strongly recommended for the management of neutropenia and febrile neutropenia (Smith 2015). There is currently no known antidote for an overdose of LV.
- Notify the medical monitor as soon as they become aware of the overdose, to discuss details of the overdose (eg, exact amount of LV administered, subject weight) and AEs, if any.

5.5.2.2. Pembrolizumab Overdose

For this trial, an overdose will be defined as ≥ 1000 mg (5 times the dose) of pembrolizumab. No specific information is available on the treatment of overdose of pembrolizumab. In the event of an overdose, the site should notify the sponsor as soon as they are aware of the overdose. The patient should be observed closely for signs of toxicity. Appropriate supportive treatment should be provided if clinically indicated.

5.5.3. Management of Overlapping Toxicities

The IBs for LV and pembrolizumab individually describe AEs commonly observed relative to individual study treatments, as well as less common serious findings. The respective IBs should be referenced when attributing causality; however, the final decision regarding causality is at the discretion of the investigator.

5.5.4. Supportive Care Guidelines for Pembrolizumab

Patients should receive appropriate supportive care measures as deemed necessary by the treating investigator. Suggested supportive care measures for the management of AEs with potential immunologic etiology are outlined along with the dose modification guidelines in Section 5.3.4. Where appropriate, these guidelines include the use of oral or IV treatment with corticosteroids, as well as additional anti-inflammatory agents if symptoms do not improve with administration of corticosteroids. Note that several courses of steroid tapering may be necessary as symptoms

may worsen when the steroid dose is decreased. For each disorder, attempts should be made to rule out other causes such as metastatic disease or bacterial or viral infection, which might require additional supportive care. The treatment guidelines are intended to be applied when the investigator determines the events to be related to pembrolizumab.

Note: If after the evaluation of the event, it is determined not to be related to pembrolizumab, the investigator does not need to follow the treatment guidance. Refer to Section 5.3.4 for guidelines regarding dose modification and supportive care.

It may be necessary to perform conditional procedures such as bronchoscopy, endoscopy, or skin photography as part of evaluation of the event.

5.6. Management of Hyperglycemia

Investigators should monitor blood glucose levels and are advised to perform additional assessments if any symptoms of hyperglycemia are observed, including a thorough evaluation for infection. In addition, if steroids are used to treat any other condition, blood glucose levels may require additional monitoring. If elevated blood glucose levels are observed, subjects should be treated according to local standard of care and referral to endocrinology may be considered.

Subjects, especially those with a history of or ongoing diabetes mellitus or hyperglycemia, should be advised to immediately notify their physician if their glucose level becomes difficult to control or if they experience symptoms suggestive of hyperglycemia such as frequent urination, increased thirst, blurred vision, fatigue, and headache.

Subjects who enter the study with elevated hemoglobin A1c (HbA1c) ($\geq 6.5\%$) or fasting glucose (≥ 126 mg/dL or ≥ 7 mmol/L) at screening should receive glucose management prior to or within 1 week of starting study treatment.

Blood glucose may be measured by blood glucose meter or laboratory-performed blood glucose test.

- Part A: random blood glucose should be checked prior to dosing on Day 1 of each 21-day cycle.
- Part B: random blood glucose should be checked prior to dosing on Days 1, 8, and 15 of the first 2 cycles. For Cycle 3 and later, blood glucose should be checked on Day 1 of each cycle, and may be checked on Day 8 and/or Day 15 if clinically indicated for subjects at risk of hyperglycemia.
- Part C: random blood glucose should be checked prior to dosing on each dosing day of the first 2 cycles. For Cycle 3 and later, blood glucose should be checked on Day 1 of each cycle, and may be checked on Day 8 and/or Day 15 if clinically indicated for subjects at risk of hyperglycemia.

Parts A, B, and C: If blood glucose is >250 mg/dL or >13.9 mmol/L, testing may be repeated on same day of dosing. LV dose may be delivered on the same day when blood glucose has decreased to 250 mg/dL or lower and the subject is clinically and metabolically stable. LV should be withheld if repeated blood glucose is >250 mg/dL or >13.9 mmol/L (non-fasting or fasting).

Note: For AE reporting purposes, the severity of hyperglycemia in the NCI CTCAE, version 5, is graded by the medical management required to address hyperglycemia and not by the value of glucose measurement.

5.7. Treatment Compliance

IV administration of LV will be performed by study site staff and documented in source documents and the case report form (CRF).

For Part C, IV administration of pembrolizumab will be performed by study site staff and documented in source documents and the CRF.

6. STUDY ACTIVITIES

6.1. Schedule of Events

A schedule of events is provided in [Appendix A](#) for baseline/screening and in [Appendix B](#), [Appendix C](#), and [Appendix D](#) for treatment. Study activities are listed by visit in this section and descriptions of all study assessments are presented in Section 7. AEs and concomitant medications will be recorded from Day 1 (predose) through the safety-reporting period (end of treatment [EOT] visit or 30 days after the last study treatment, whichever is later, with the exception of AEs of interest, which will be followed until resolution, death, or withdrawal of consent; see Section 7.6.1.3). Any study protocol-related AE (defined in Section 7.6.1.1) as well as any concomitant medications given for the treatment of the AE, should be recorded from the time of informed consent.

